6 RESPONSE ASSESSMENTS

Refer to [Section 10.2](#) of the Core ([Appendix A](#)) for complete instructions regarding response assessments.

The Sponsor or designee will collect all study scans for possible independent review and analysis. Skin lesions must be photographed along with a ruler at all time points for tumor assessments.

6.1 Part A

- The primary criterion for defining evidence of anticancer activity is RECIST v1.1. The criterion for management of subject care and treatment discontinuation is irRECIST.
- Tumor assessments will be completed by CT or MRI at Screening, q8w (± 1 week) from Cycle 1 Day 1 for 12 months, and q12w (± 1 week) thereafter until confirmed progression as assessed by irRECIST.
- Any subject with a complete response or partial response is to have repeat assessments performed as early as 4 weeks after initial observation of response to confirm the response as defined by RECIST 1.1
- At the first occurrence of progressive disease, as defined by RECIST 1.1, the baseline is reset and overall response as assessed by irRECIST will be noted as immune-related stable disease. Immune-related progressive disease is determined only if an increase in tumor burden of 20% relative to the new baseline is observed on a subsequent tumor assessment.

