1 INTRODUCTION AND BACKGROUND INFORMATION

This study is composed of 2 distinct documents:

- [REDACTED]
- This CX-072-specific Module (CTMX-M-072-002)

Briefly, [REDACTED], or [REDACTED] is a stable document that contains all study design features typically included in a standard Phase 1-2 clinical study protocol, but without reference to a specific investigational medicinal product (IMP). The Core, which provides the basis for all first in human clinical studies with ProbodTM therapeutics, describes general study procedures such as guidelines for drug accountability, efficacy and safety parameters, and study administrative procedures. The CX-072 Module for this Phase 2 study (this document) is customized for the assessment of the CX-072 ProbodTM therapeutic in combination with ipilimumab at the designated combination doses and provides all guidelines necessary to safely manage subject care. Familiarity with both documents is required for proper conduct of this study.

This core plus module system will enable a comprehensive clinical evaluation of ProbodTM therapeutics within a unified clinical development program that has common components of study design, execution, and assessments, and common Investigator oversight. Where there are overlapping directives between the 2 documents, Investigators are instructed to follow the CX-072 Module regarding subject care guidelines. [REDACTED] for a more detailed discussion of the Core study design and rationale.

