3.7 Estimated Treatment Duration and Study Periods

In Part A, a subject's treatment may continue until confirmed disease progression (assessed by irRECIST), clinical deterioration as defined by the Investigator, withdrawal of consent, other study treatment withdrawal criteria are met, or until the study is terminated, whichever occurs first. In Part B, a subject's treatment duration will continue until progression as defined by RECIST prior to surgery, disease relapse after surgery, clinical deterioration as defined by the Investigator, withdrawal of consent, other study treatment withdrawal criteria are met, the subject has received CX-072 for 1 year postsurgery, or until the study is terminated, whichever occurs first. In Part B, a subject's treatment duration will be up to approximately 15 months (including 1 year postsurgery).

This Module is comprised of 3 periods:

- The Screening Period begins within 30 days prior to the first dose of study treatment (ie, Cycle 1 Day 1 Visit). Subjects for whom consent is provided will undergo Screening Period assessments to determine eligibility for the study; assessments must be performed within 30 days prior to the first dose of study treatment unless otherwise stated in this Module. Subject evaluations and tests performed specifically to determine eligibility (ie, not performed as routine standard of care) may be performed only after the informed consent form (ICF) has been signed. Assessment(s) done per standard of care prior to signing the ICF may be used for eligibility determination if completed within 30 days prior to the first dose of study treatment. The study assessments to be followed are outlined in the Schedule of Assessments in [Table 1](#) (Part A) and [Table 2](#) (Part B).
- The Treatment Period begins with the first dose of study treatment (ie, Cycle 1 Day 1) and continues up to 30 days after the last dose of study treatment (ie, End of Treatment [EOT] Visit). All scheduling is relative to first dose of study treatment (ie, Cycle 1 Day 1).

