4.11 Study Treatment Discontinuation Criteria

Subjects MUST discontinue study treatment for any of the following reasons:

- The subject experiences confirmed disease progression as assessed by irRECIST (Part A) or disease progression prior to surgery or disease relapse after surgery (Part B)
- The subject is unwilling or unable to adhere to the protocol
- The subject withdraws consent or is lost to follow-up
- The subject experiences an adverse event (AE) that precludes further safe administration of study treatment (see also [Section 5.3.1](#))
- The subject becomes pregnant at any time during the study, including prior to the first dose of study treatment
- In the Investigator's judgment, the subject should discontinue study treatment
- The Sponsor terminates the study
- The subject experiences an intercurrent illness that prevents further administration of study treatment
- The subject requires new/other anticancer treatment

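### Section 6.1 measures irRECIST progression from the reset baseline, so, read literally, the Part A imaging stop loosens for subjects who shrink after the reset and then relapse

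*Combined protocol and SAP*

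**What the plan says.** For Part A, Section 6.1 separates two roles. RECIST v1.1 defines evidence of activity. For treatment decisions: "The criterion for management of subject care and treatment discontinuation is irRECIST".

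The rule for progression then runs in two steps. "At the first occurrence of progressive disease, as defined by RECIST 1.1, the baseline is reset and overall response as assessed by irRECIST" is recorded as immune-related stable disease. After that, "Immune-related progressive disease is determined only if an increase in tumor burden of 20% relative to the new baseline is observed" on a later assessment. The Module text does not mention a nadir or a lowest burden after the reset.

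Several other provisions depend on this rule:
- Section 4.11 makes confirmed irRECIST progression a mandatory reason to stop treatment in Part A.
- Section 5.2.2 continues CX-072 monotherapy every 2 weeks until irRECIST progression, unacceptable toxicity or another discontinuation criterion.
- Section 6.1 continues scans (every 8 weeks for 12 months, then every 12 weeks) until confirmed irRECIST progression.

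Two provisions bear on how 6.1 should be read. Section 6 refers to Core Section 10.2 "for complete instructions regarding response assessments", and Section 2.2 says that irRECIST is defined in the Core. Section 1 adds: "Where there are overlapping directives between the 2 documents, Investigators are instructed to follow the CX-072 Module regarding subject care guidelines".

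**The concern.** Recording first progression as immune-related stable disease lets treatment continue past it, which allows for subjects whose tumors shrink late. Those are the subjects for whom the choice of reference matters. If the 20% is always measured from the reset value, the deeper the later shrinkage, the more regrowth is needed before the imaging stop applies.

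What is at stake is time on treatment after a second relapse. Part A has no maximum treatment duration, and Section 5.6 allows new anticancer therapy only after the last study dose. Each further scan interval spent below the threshold corresponds to 8/2 = 4 doses in the first 12 months, or 12/2 = 6 doses after that, unless another stop applies.

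**Working it through.** There is no calculated figure in the plan to reproduce; the 20% is a rule.

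**Inputs**
- Threshold: a 20% increase over the reset baseline (Section 6.1).
- Reset value R: 100 mm, chosen for illustration.
- Shrinkage s from R to the post-reset low: 0% to 50%, assumed. The documents give no distribution for it.

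**Formulas**
- Post-reset low: L = (1 - s)R
- Threshold as written: 1.2R
- Regrowth needed from the low, as written: 1.2R/L - 1 = 1.2/(1 - s) - 1
- Threshold with a later-low reference: 1.2(1 - s)R
- Difference in thresholds: 1.2R - 1.2(1 - s)R = 1.2sR

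**Results for R = 100 mm**

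| s | Low (mm) | Threshold as written (mm) | Regrowth needed as written | Later-low threshold (mm) | Difference (mm) |
|---|---|---|---|---|---|
| 0% | 100 | 120 | 20% | 120 | 0 |
| 10% | 90 | 120 | 33.3% | 108 | 12 |
| 20% | 80 | 120 | 50% | 96 | 24 |
| 30% | 70 | 120 | 71.4% | 84 | 36 |
| 40% | 60 | 120 | 100% | 72 | 48 |
| 50% | 50 | 120 | 140% | 60 | 60 |

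With s = 30%, for example, 1.2/0.7 - 1 = 71.4%. The percentages do not depend on R. With no shrinkage after the reset, the two references give the same threshold.

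**Does the Core settle it?** There are two possibilities:
- If the Core measures from the later low, it differs from 6.1. Treatment discontinuation is subject care in 6.1's own terms, so the precedence sentence in Section 1 points sites to the Module's looser rule.
- If the Core also measures from the reset value, both documents share the weakness.

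Either way, sites would be helped by 6.1 naming the reference point.

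**The case against.** The strongest objection is that 6.1 is a summary and the Core holds the definition. Section 2.2 assigns the irRECIST definition to the Core, and Section 6 refers there for full instructions. Section 6.1 says nothing about new lesions, non-target lesions or how progression is confirmed, although 4.11 requires confirmation. A bullet that leaves so much to the Core may leave the reference point there too. It can also be read as covering only the scan right after the reset, when the new baseline is the only post-reset value and both references agree. The precedence sentence applies only if the Core actually differs.

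This stands in part. It rules out saying that the trial's irRECIST definition is wrong. It does not remove the ambiguity: the sentence is worded as an exclusive condition, names one reference, and refers to a subsequent assessment without limiting it to the next one.

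The second objection is that other exits exist, and this stands. Section 4.11 also requires a stop when "In the Investigator's judgment, the subject should discontinue study treatment", or when the subject needs other anticancer treatment. Section 3.7 lets treatment run until "confirmed disease progression (assessed by irRECIST), clinical deterioration as defined by the Investigator", or another listed reason, whichever comes first. A reader might infer that relapsing subjects are held on study drug until they regrow by 71%. The documents do not support that: the imaging rule is one of several stops, and the limit on new therapy in Section 5.6 does not keep anyone on treatment. The other exits do rest largely on judgment or symptoms, so they do not replace a uniform imaging rule in an open-label study at about 40 sites.

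**Conclusion.** The point holds in a limited form and is minor. Read literally, 6.1 makes the imaging-based mandatory stop, and the scan schedule tied to it, less sensitive as post-reset shrinkage deepens: 33% regrowth from the low after 10% shrinkage, 71% after 30% and 140% after 50%, against 20% with a later-low reference. The arithmetic is exact, but the shrinkage values are assumptions and the number of affected subjects is unknown. Subjects who do not shrink after the reset are unaffected.

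The conclusion rests on reading 6.1 as the operative rule for later scans as well as the next one. The Core could show that a different rule was intended, though the precedence sentence would still need attention.

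A reader might also infer that the efficacy results are biased. The documents do not support this for the primary endpoint: ORR is judged by RECIST v1.1, which this rule does not alter. No effect on the secondary endpoints is claimed, because their methods are in the Core.

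**What to change.** In the last sentence of the progression bullet in 6.1, replace the new baseline as the reference with *the smallest tumor burden recorded at or after the new baseline*, and check the wording against Core Section 10.2 so that the two documents agree. Leave the rules on confirmation, new lesions and non-target lesions to the Core.

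Do not add an absolute minimum increase, such as 5 mm, unless the Core has one. Nothing in the available documents supports it, and it would delay the stop slightly in small-volume disease. With a 20 mm reset value and no shrinkage, the threshold would be 20 + 5 = 25 mm instead of 1.2 x 20 = 24 mm.

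The cost is one phrase in an amendment and a cross-check, with no added scans, visits or subjects. The downside is that a few subjects with modest regrowth from a post-reset low would reach the mandatory stop earlier than under the present wording.

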6.2 Part B

- The primary criterion for defining evidence of anticancer activity is pathologic response based on central review of tumor sample from surgical resection. The criteria for management of subject care and treatment discontinuation are radiographic response assessment (prior to surgery), local pathologic assessment of surgical sample after surgery, or disease relapse. Tumor response, as defined by RECIST v1.1, will be assessed prior to surgical resection; however, responses will not be confirmed because the tumor assessment will be followed by surgical resection.
- Pathologic analysis of the resected tumor will be conducted by central review and according to the International Neoadjuvant Melanoma Consortium (INMC) scoring system ([Tetzlaff 2018](#))
 - Pathologic complete response (pCR): Complete absence of viable tumor
 - Major pathologic response/near pCR: >0% but <10% of viable tumor in the treated tumor bed
 - Pathologic partial response (pPR): ≤50% of the treated tumor bed is occupied by viable tumor cells
 - Pathologic nonresponse (pNR): >50% of the tumor bed occupied by viable tumor cells
- Relapse is defined as the recurrence of melanoma locally, regionally, with distant metastasis, or with a new primary lesion
- Tumor assessments will be completed by CT or MRI at Screening, prior to scheduled surgical resection (ie, Cycle 1 Day 40 ±2 days), after completion of combination treatment following surgery (ie, Cycle 2 Day 22 [Study Day 106] ±2 days), and then every 12 (±1) weeks until relapse. After 3 years, tumor assessments will be performed according to standard of care.
- Prior to surgical resection, responses noted at the time of the tumor assessment will not be confirmed by a subsequent tumor assessment because the subject will undergo surgery following the presurgical tumor assessment

7 SAFETY ASSESSMENTS

Incidence and nature of AEs and SAEs (as assessed according to CTCAE Version 5.0) as well as physical examinations, vital sign measurements, ECGs, clinical laboratory evaluations, and treatment discontinuation due to toxicity will be evaluated for safety assessment. Safety assessments will also include tests for immunogenicity as described in [Section 8.3](#).

Safety assessments will be performed in accordance with the Schedule of Assessments [Table 1](#) (Part A) and [Table 2](#) (Part B). Refer to the footnotes below the tables, applicable sections with this Module, and the Core ([Appendix A](#)) for a description of each procedure.

Subjects will continue to be monitored for irAEs, AEs \geq Grade 3, and SAEs up to 90 days following their last dose of study treatment. Toxicity management may require additional visits at the discretion of the Investigator. Additional follow-up will occur for subjects with ongoing AEs, SAEs, or AEs of special interest (AESIs) unless events have returned to baseline or stabilized.

8 PHARMACOKINETIC, IMMUNOGENICITY, AND EXPLORATORY BIOMARKER ASSESSMENTS

8.1 Pharmacokinetic Assessments

Concentration versus time data will be tabulated and plotted for the individual and mean serum total and intact CX-072 moieties. C_{\max} and C_{\min} will be tabulated individually and summarized using descriptive statistics (eg, mean, standard deviation, and coefficient of variation).

Ipilimumab C_{\max} and C_{\min} will be summarized using descriptive statistics.

Population PK (POPPK) analysis of the data may be performed as warranted by the data and results of the analysis will be reported separately.

8.2 Pharmacokinetic Sample Collection

Samples should be drawn from a site other than the infusion site (ie, contralateral arm) on days of infusion (see Schedule of Assessments Table 1 [Part A] and Table 2 [Part B]). The schedule of PK blood sampling for both Part A and Part B can be found in [Table 3](#); the times noted are predose or at the end of infusion (EOI).

The date and time of each dose administered and the times at which PK samples are collected must be recorded in the eCRF. If the infusion was interrupted, the reason for interruption will also be documented in the eCRF, and a sample will be collected at the EOI.

8.3 Immunogenicity Assessments

Serum samples will be collected to assess the immunogenicity of CX-072 and ipilimumab (Schedule of Assessments [Table 1](#) [Part A] and [Table 2](#) [Part B]). All samples will be initially screened for ADAs. If the sample is found to be ADA positive in the screening assay, a confirmatory assay will be performed. Confirmed ADA positive samples will be evaluated with a titer assay and may be further characterized for the presence of neutralizing or domain-specific ADA.

[figure not shown]
8.5 Exploratory Biomarker Collection

To address the above objectives, archival tumor tissue and blood samples will be collected at various time points as shown in the Schedule of Assessments Table 1 (Part A) and Table 2 (Part B).

8.5.1 Tumor Tissue

In Part A, tumor samples for biomarker assessments will be collected during Screening (archival or fresh biopsy). Fresh biopsies are required for subjects who do not have archival tumor samples and optional for subjects with accessible lesions that can be safely biopsied. The most recently obtained tumor sample should be provided for analysis.

In Part B, archival tumor samples from the initial diagnostic biopsy will be collected during Screening. Tumor tissue from surgical resection (including resected lymph nodes) during the study will also be collected.

8.5.2 Blood Samples

Blood collection is mandatory for all subjects. Samples should be drawn from a site other than the infusion site (ie, contralateral arm) on days of infusion. The full schedule of biomarker blood sampling can be found in Schedule of Assessments [Table 1](#) (Part A) and [Table 2](#) (Part B).

The date and time of each dose administered and the times at which blood biomarker samples are collected must be recorded in the eCRF.

The technical details for the collection of specimens are outlined in the study laboratory manual.

9 ADVERSE EVENTS/ SERIOUS ADVERSE EVENTS AND REPORTING

9.1 Adverse Events

An AE is defined as any unfavorable and/or unintended sign (including an abnormal laboratory finding), symptom, or disease temporally associated with the use of an IMP, whether or not related to the IMP.

All AEs within the reporting period (as defined below) are to be recorded in the AE eCRF. Nonserious AEs prior to initiation of study treatment will be recorded as medical history. Whenever possible, it is preferable to record a diagnosis as the AE term rather than a series of terms relating to a diagnosis.

The reporting period for AEs is as follows:

- After the ICF is signed but prior to the initiation of study treatment, only SAEs will be reported
- After the ICF is signed and the first administration of study drug, all nonserious AEs and SAEs are reportable and continue to be reported up to 30 days after the last dose of study drug
- During the Follow-up Period, AE reporting is limited to irAEs, AEs \geq Grade 3, and SAEs occurring up to 90 days after last dose of study drug

After the defined AE reporting period, all SAEs assessed as related to study treatment will be reported to the Sponsor. At the last scheduled visit, the Investigator must instruct each subject to report to the Investigator and/or Sponsor or designee, any subsequent SAE that the subject's personal physician(s) believes might be related to prior study treatment. The Investigator must notify the study Sponsor or designee of any death or SAE that may have been related to prior study treatment.

For this Module, disease progression is an efficacy endpoint and in and of itself is not considered an AE or SAE unless disease progression results in death. Death that occurs during the AE reporting period (as defined above), that is attributed solely to disease progression of the

condition, will be recorded in the AE eCRF as a Grade 5 AE (regardless of attribution to study treatment). Deaths reported as SAEs due to progressive disease and considered not related to study treatment will be excluded from TEAE analysis.

All AEs (including SAEs), whether or not related to study drug, must be fully and completely documented using precise medical terminology in the applicable eCRFs (eg, AE eCRF, drug dispensation eCRF).

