5.2 Study Drug Administration and Dosing Regimen

5.2.1 Study Drug Administration

5.2.2 Study Treatment Dosing Regimen

CX-072 and ipilimumab are to be administered in this study as follows:

- Part A:
 - Combination treatment: 800 mg CX-072 + 3 mg/kg ipilimumab, q3w
 - Monotherapy treatment: 800 mg CX-072, q2w
- Part B:
 - Combination treatment: 800 mg CX-072 + 1 mg/kg ipilimumab, q3w
 - Monotherapy treatment: 800 mg CX-072, q2w

In Part A, subjects will be treated with 4 doses of 800 mg CX-072 IV plus 3 mg/kg ipilimumab IV combination therapy (ie, q3w on Cycle 1 Day 1, Cycle 1 Day 22, Cycle 2 Day 1 [Study Day 43], and Cycle 2 Day 22 [Study Day 64]; all ± 2 days). Three weeks following receipt of the fourth dose of combination treatment (ie, Study Day 85 [± 2 days]), subjects will receive 800 mg CX-072 IV monotherapy q2w until the occurrence of progressive disease by irRECIST, unacceptable toxicity, or the subject meets any other criterion for treatment discontinuation (Section 4.11).

In Part B, subjects will be treated with 2 doses of 800 mg CX-072 IV plus 1 mg/kg ipilimumab IV combination (ie, q3w on Cycle 1 Day 1, Cycle 1 Day 22; all ± 2 days) followed by surgical resection of the tumor on Day 43 (-2/+7 days). An additional 2 doses of 800 mg CX-072 IV plus 1 mg/kg ipilimumab IV combination will be administered approximately 6 weeks postsurgery (ie, q3w on Cycle 2 Day 1 [Study Day 85 (± 2 days)] and Cycle 2 Day 22 [Study Day 106 (± 2 days)]). Three weeks following receipt of the fourth dose of combination treatment (ie, Study Day 127 [± 2 days]), subjects will have the option to continue with 800 mg CX-072 IV monotherapy q2w following discussion and agreement of risk/benefit between the Investigator and the Sponsor Medical Monitor. Subjects may receive up to 1 year of CX-072 infusions postsurgery (including 2 postsurgery combination doses and then as monotherapy) until the occurrence of disease relapse, unacceptable toxicity, or the subject meets any other criterion for treatment discontinuation ([Section 4.11](#)).

A maximum of 4 doses of ipilimumab may be administered to any subject (Parts A and B).

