9.5 Documentation of Adverse Events by Investigator

Subjects will be evaluated and questioned generally to identify AEs during the course of the study. Any nonserious AEs occurring after signing the ICF and prior to administration of the first dose of study drug will be recorded in the medical history eCRF. Events occurring after administration of the first dose of study drug will be recorded in the AE eCRF. AEs that occur up to 30 days after administration of the last dose of study drug must be reported as AEs in the EDC system. Additionally, all irAEs, AEs \geq Grade 3, and SAEs that occur up to 90 days after administration of the last dose of study drug must be reported in the EDC system. See also [Section 9.6](#) for reporting of SAEs.

All AEs spontaneously reported by the subject and/or in response to an open question from study personnel or revealed by observation, physical examination, or other diagnostic procedures will be recorded in the AE eCRF. Wherever possible, a specific disease or syndrome rather than individual associated signs and symptoms should be identified. However, if an observed or reported sign or symptom is not considered a component of a specific disease or syndrome by the Investigator, it should be recorded as a separate AE.

Any clinically relevant deterioration in laboratory assessments or other clinical findings is considered an AE and must be recorded in the AE eCRF. Clinical syndromes associated with laboratory abnormalities are to be recorded as appropriate (eg, diabetes mellitus rather than hyperglycemia). In addition, an abnormal test finding will be classified as an AE if 1 or more of the following criteria are met:

- The test finding is accompanied by clinical symptoms
- The test finding necessitates additional diagnostic evaluation(s) or medical/surgical intervention; including significant additional concomitant drug treatment or other therapy.
Note: Simply repeating a test finding, in the absence of any of the other listed criteria, does not constitute an AE
- The test finding leads to a change in study drug dosing or discontinuation of subject participation in the clinical research study
- The test finding is considered an AE by the Investigator

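### In Part B, all-grade adverse event reporting is tied to the last dose and not to surgery, so for operated subjects who do not restart it closes nominally 9 days after the operation, or before it after a single dose

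*Combined protocol and SAP*

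**What the plan says.** Section 9.1 (Adverse Events) sets the reporting period for both Parts. From the first dose, "all nonserious AEs and SAEs are reportable and continue to be reported up to 30 days after the last dose of study drug". In follow-up, only irAEs, AEs of Grade 3 or higher and "SAEs occurring up to 90 days after last dose of study drug" are reportable. After that, only SAEs judged related to treatment are reported. Section 9.5 repeats the first limit: "AEs that occur up to 30 days after administration of the last dose of study drug must be reported as AEs in the EDC system". Section 7 repeats the 90-day rule. Section 3.7 uses the same anchor for the Treatment Period, which "continues up to 30 days after the last dose of study treatment", when the End of Treatment (EOT) Visit takes place. Section 5.6 narrows concomitant medication recording after EOT to treatment of irAEs, AEs of Grade 3 or higher and SAEs.

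For Part B, Section 5.2.2 schedules two combination doses ("q3w on Cycle 1 Day 1, Cycle 1 Day 22; all ± 2 days"), "followed by surgical resection of the tumor on Day 43" with a window of 2 days before to 7 days after. Two further doses follow, which "will be administered approximately 6 weeks postsurgery", starting on Study Day 85. Section 5.3 requires at least 21 days between ipilimumab infusions and lets an infusion be delayed by up to 7 days in exceptional circumstances.

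Sections 7, 9.1, 9.5 and 9.6.1 do not mention the operation. Section 7 does refer to Table 2 and the Core for safety assessments. Neither could be read.

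**The concern.** Surgery is a planned study step, and in Part B it falls in a gap of about nine weeks between doses 2 and 3. A subject who restarts on Day 85 is under all-grade reporting through the operation and recovery. A subject who does not restart has a last dose on Day 22 or Day 1, and the 30-day limit then falls close to the operation or before it.

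The plan foresees such subjects. Section 6.2 lists local pathologic assessment of the surgical specimen among the Part B criteria for discontinuing treatment. Section 4.11 requires stopping for relapse after surgery or for an AE that precludes further treatment.

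Safety and tolerability is a Part B secondary objective (Section 2.2.1), and better tolerability is the rationale for the combination (Section 1.4). If low-grade postoperative events are recorded for restarters but not required for others, the all-grade rates mix two lengths of observation. A complication or toxicity may itself be the reason for not restarting, so the shorter observation may not be random.

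**Working it through.** The plan gives no figure for when reporting closes relative to surgery, so the check is day arithmetic on its schedule.

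**Inputs**
- Dose 1: Day 1. Dose 2: Day 22 ± 2, so Day 20 to 24 (Section 5.2.2).
- Surgery: Day 43, -2/+7, so Day 41 to 50 (Section 5.2.2).
- Restart: Day 85 ± 2 (Section 5.2.2).
- All AEs: to last dose + 30 days (Sections 9.1, 9.5).
- irAEs, Grade 3 or higher, SAEs: to last dose + 90 days (Sections 7, 9.1, 9.5).
- At least 21 days between ipilimumab infusions; delay of up to 7 days permitted (Section 5.3).

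**Timeline check.** 85 - 43 = 42 days = 6 weeks, which matches the stated restart interval.

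**Formula.** Days from surgery to closure = (last dose day + window) - surgery day. A negative result means closure before surgery.

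| Last dose before not restarting | All-grade closure | Relative to surgery |
|---|---|---|
| Day 22, surgery Day 43 (nominal) | 22 + 30 = Day 52 | 52 - 43 = 9 days after |
| Day 20 to 24 (stated windows) | Day 50 to 54 | 50 - 50 = 0 to 54 - 41 = 13 days after |
| Day 22 to 24 (21-day minimum applied) | Day 52 to 54 | 52 - 50 = 2 to 54 - 41 = 13 days after |
| Up to Day 29 (7-day delay) | up to Day 59 | up to 59 - 41 = 18 days after |
| Day 1 only | 1 + 30 = Day 31 | 31 - 41 = -10 to 31 - 50 = -19, so 10 to 19 days before |

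The lower limit of 0 needs dose 2 on Day 20, which the Section 5.2.2 window allows and the 21-day minimum in Section 5.3 does not. Those two sections must be reconciled.

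**What stays covered**
- Last dose Day 20 to 24: to Day 110 to 114, which is 110 - 50 = 60 to 114 - 41 = 73 days after surgery (nominal 112 - 43 = 69).
- Day 1 only: to Day 91, which is 91 - 50 = 41 to 91 - 41 = 50 days after surgery.

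**What falls out.** After closure, new events that are Grade 1-2, nonserious and not immune-related need not be recorded. Following ongoing AEs (Sections 7 and 9.4) does not bring in new ones. Under Section 5.6, medication given for such an event is not recorded after EOT either.

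**Effect of a surgery-linked limit.** Surgery + 30 days gives Day 41 + 30 = 71 to 50 + 30 = 80 (nominal 73). The gain equals surgery day minus last dose day: 41 - 24 = 17 to 50 - 20 = 30 days (nominal 43 - 22 = 21). After a single dose it is 41 - 1 = 40 to 50 - 1 = 49 days. In these cases the limit lies inside the existing 90-day window (80 is less than 91 and 110), so that window needs no change.

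**The case against.** The strongest reply is that clinically important surgical morbidity is already captured. Grade 3 or higher events, irAEs and SAEs are collected for weeks after the operation even after a single dose, and Section 9.1.1 counts any event that requires or prolongs hospitalization as serious. This stands. A reader might infer that AE collection as a whole stops around surgery; the documents do not support that. The gap is confined to low-grade, nonserious, non-immune events in operated subjects who do not restart.

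Second, Table 2 and the Core are unseen, and a postsurgical safety visit could sit there. This also stands as a limit. It does not remove the point, because Sections 9.1 and 9.5 define the reporting period and contain no such extension.

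Third, unless stopping is decided earlier, on Day 52 nobody knows that Day 22 was the last dose, so sites may still be recording everything. That probably narrows the gap in practice, but the written rule does not require those entries.

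Fourth, one might infer that subjects who do not restart are mainly those with surgical complications, and that Part B rates are therefore shown to be biased low. The documents give neither the number nor the reasons. Subjects judged ineligible for surgery because of progression or toxicity (Section 10.2) have no study operation and lose no surgical events. Selective loss is plausible, not demonstrated.

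Fifth, surgical morbidity is not a named endpoint, and the 30/90-day structure is applied consistently. That is fair, and it limits the importance of the point. Even so, the all-grade safety summary should not depend on restarting by accident of the schedule.

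**Conclusion.** The point holds in limited form. Followed exactly, Sections 9.1 and 9.5 close all-grade reporting nominally 9 days after surgery in an operated Part B subject who does not restart. The range is 0 to 13 days on the stated windows, 2 to 13 with the ipilimumab minimum, and up to 18 with a delayed second dose. After a single dose, closure comes 10 to 19 days before the operation. Subjects who restart on Day 85 have no gap.

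Any effect on the reported all-grade rates can only be downward, since events are omitted and none are added. Its size cannot be derived, because the number of non-restarters and their rate of low-grade events are not given.

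This rests on three assumptions: surgery takes place in its stated window even after one dose, some operated subjects do not restart, and neither Table 2 nor the Core extends the reporting period after surgery. It is a worthwhile, inexpensive improvement to data collection, not a defect that threatens the trial's primary result.

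**What to change.** In Sections 9.1 and 9.5, state that for Part B subjects who undergo study surgery, all AEs are reported until the later of 30 days after the last dose and 30 days after surgery. The 30 days after surgery is a proposed figure that mirrors the existing post-dose period. Align the Part B EOT Visit (Section 3.7), concomitant medication recording (Section 5.6) and Table 2 with it. If Table 2 or the Core already contains a surgery-linked AE provision, cite it in Sections 9.1 and 9.5. Leave the 90-day window for irAEs, AEs of Grade 3 or higher and SAEs unchanged. Separately, reconcile the dose 2 window in Section 5.2.2 with the minimum interval in Section 5.3.

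The cost is a short amendment touching several sections, some extra AE and medication entries for what is likely a small number of subjects, and possibly slightly higher reported AE rates in Part B. Treatment and clinical management do not change.
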